### **6.3.3 Treatment-Related Adverse Events**

Assessment of relatedness to study drug for all AEs will be classified by investigators and reported. “Definitely related”, “probably related” and “possibly related” AEs will be considered as treatment related. An AE will be assigned as treatment-related if the relationship to study drug cannot be determined.

The incidences of treatment-related AEs will be presented by MedDRA SOC and PT with any grade and with Grade 3 or 4.

### **6.3.4 Serious Adverse Events**

SAEs are defined (21 CFR 312.32, ICH of Technical Requirements for Registration of Pharmaceuticals for Human Use E2A Guideline) as those AEs that meet any of the following criteria:

- Results in death.
- Is life-threatening: ie, any event that, in the opinion of the Investigator, poses an immediate risk of death from that event.
- Requires inpatient hospitalization or prolongation of existing hospitalization (excluding hospitalizations for study therapy, disease-related procedures, or placement of an indwelling catheter, unless associated with other SAEs).
- Results in a persistent or significant disability/incapacity.
- Results in a congenital anomaly/birth defect.
- Includes important medical events that may not be immediately life threatening or result in death or hospitalization but may jeopardize the patient or may require intervention to prevent one of the outcomes listed in this definition.

Listing of all SAEs will be provided. Treatment-emergent SAEs and treatment-related SAEs will be summarized by MedDRA SOC and PT with any grade and with Grade 3 or 4.

### **6.3.5 Maximum Severity of Adverse Events**

TEAEs and treatment-related AEs will be summarized by MedDRA SOC, PT, and maximum CTCAE severity grade. AEs with a missing severity grade will not be included in these analyses. Patients who experience the same event at more than one severity level will be counted only once under the maximum severity level.

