#### 3.3.3 Handling of Missing Data

Missing data will not be imputed. All data will be presented as collected.

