### 6.3.2 Treatment-Emergent Adverse Events

TEAEs are AEs that occur from the first dose of study treatment until 35 (±5) days after the last dose of study treatment. If it cannot be determined whether an AE is treatment-emergent (based on start date or, if the start date is missing then based on the stop date), then the AE will be considered treatment-emergent.

Summary of TEAEs by MedDRA SOC and PT will be presented with any grade and with Grade 3 or 4. Patients who experience more than one type of AE will be counted under each of the corresponding PTs. Patients who experience different episodes of the same AE will be counted only once under the corresponding PT. Similarly, for determination of MedDRA SOC incidences, patients who experience multiple AEs under the same SOC will be counted only once for that SOC. Listing of all TEAEs will also be provided.

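### Events with a missing grade are left out of the maximum-severity tables, a one-directional exclusion that a 'grade missing' category would remove

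*SAP*

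**What the plan says.** SAP Section 6.3.5 sets up the tables: "TEAEs and treatment-related AEs will be summarized by MedDRA SOC, PT, and maximum CTCAE severity grade". It then excludes ungraded events from them: "AEs with a missing severity grade will not be included in these analyses". Within a patient the counting rule is "Patients who experience the same event at more than one severity level will be counted only once under the maximum severity level". Section 6.3.5 provides no category for a missing grade, no count of what was excluded and no sensitivity analysis.

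Three other rules bear on the point:

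- **Unknown timing (6.3.2).** If it cannot be settled whether an event is treatment-emergent, "then the AE will be considered treatment-emergent".
- **Unknown relatedness (6.3.3).** "An AE will be assigned as treatment-related if the relationship to study drug cannot be determined".
- **Missing data in general (3.3.3).** "Missing data will not be imputed. All data will be presented as collected".

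The tables in 6.3.2 are specified as "Summary of TEAEs by MedDRA SOC and PT will be presented with any grade and with Grade 3 or 4", and 6.3.3 uses the same layout for treatment-related events. Neither section excludes ungraded events from its any-grade counts. Section 6.3.2 adds "Listing of all TEAEs will also be provided". The overall summary in 6.3.1 also has by-severity rows, for which no missing-grade rule is stated.

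**The concern.** An adverse event record can lack three things that decide where it is counted: its timing, its relationship to the drug and its grade. For the first two the SAP counts the event against the drug. For the third it removes the event from the table, and it gives no reason for the difference.

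Safety and tolerability is a secondary objective (1.2.2) and the study is single-arm (2.1). With no comparator arm in which the same loss would occur, the severity distribution is read as an absolute rate. A rule that can move that distribution only towards lower severity is then undesirable even if few events are affected. A reader who compares the maximum-grade table with the any-grade table may also find totals that differ, with nothing in the table to explain why.

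**Working it through.** The SAP states no figure to reproduce. The check applies its rules to the possible cases for one patient in one row (a preferred term or a system organ class).

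| Events the patient has in the row | Any-grade table (6.3.2, 6.3.3) | Maximum-grade table (6.3.5) |
|---|---|---|
| All graded | counted once | counted once, at the maximum grade |
| Only ungraded | counted once | absent |
| Graded and ungraded | counted once | counted once, at the maximum *recorded* grade |

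**Direction.** The maximum over a patient's recorded grades cannot exceed the maximum over all that patient's grades, recorded or not. For any grade g, the number of patients shown at or above g is therefore at most the true number. This holds for cumulative counts. The count at exactly one low grade can be too high: a patient with a Grade 1 episode and an ungraded episode that was in truth severe appears at Grade 1.

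**Gap between tables.** For any row:

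any-grade count − sum over grades = number of patients whose only events in that row are ungraded.

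Only the second case in the table contributes. Patients in the third case may be under-graded, but they are still counted once and create no gap. Comparing totals would therefore not reveal them.

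**Level of the row.** A patient with an ungraded event under one term and a graded event under another term of the same organ class is absent from the first term's row, but present in the class row at the recorded grade.

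**Size per patient.** The planned cohort sizes in 3.2.1 and 3.2.2 are 87 and 70:

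- Cohorts 1 and 2: 1/87 = 0.0115, or 1.1 percentage points.
- Cohorts 3 and 4: 1/70 = 0.0143, or 1.4 percentage points.

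If k patients are affected in a row, the largest possible shift is k/87 or k/70. The SAP gives nothing from which to derive k.

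**Does 3.3.3 require the exclusion?** No. It forbids filling in a grade. It does not call for dropping an event that has none, and presenting data as collected fits a 'grade missing' entry better than an omission.

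**The case against.** The strongest reply is that this is a matter of table layout with little behind it. Section 6.3 has the investigator grade every adverse event, so a missing grade should be an exception. The exclusion is stated in advance and touches neither the primary endpoint nor any test. Timing and relatedness are yes/no questions with a natural cautious answer, whereas a grade has several levels and no obvious default. Assigning one would also depart from 3.3.3. All of this stands. It limits the weight of the point, but it does not explain why the event has to leave the table.

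Some stronger readings are tempting and are not supported:

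- **That ungraded events vanish from the safety report.** They do not. They remain in the any-grade tables of 6.3.2 and 6.3.3 and in the listing of all treatment-emergent events. Serious ones also appear in the any-grade tables and the listing of 6.3.4. Events leading to death or discontinuation are listed separately and summarized under 6.3.6. The listings carry the grade, so a blank is visible.
- **That many grades will be missing because events are still open at a data snapshot.** Section 3.5 ties the snapshot to the primary-endpoint-only analysis, after data cleaning. It places the safety analysis at the full cohort analysis, after final database lock.
- **That the tables are bound to disagree, or that the disagreement can be put at some percentage.** They differ only if at least one patient has nothing but ungraded events in a row, and the SAP offers no rate of missing grades.
- **That the SAP contradicts itself.** It handles three unknowns in different directions, which is an uneven approach and not a contradiction.

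**Conclusion.** The point holds as a minor improvement. Section 6.3.5 contains an exclusion that can only leave unchanged or lower the severity shown in the maximum-grade tables, set beside two rules that resolve the other unknowns cautiously. Each affected patient is worth up to 1.1 points (n = 87) or 1.4 points (n = 70) in a row, on the assumption that the cohorts reach their planned size. The total is unknown and probably small; that rests on the further assumption that investigators grade nearly all events, as Section 6.3 requires. If no grade is missing, the effect is zero. No conclusion on efficacy depends on it.

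**What to change.** Replace the exclusion sentence in Section 6.3.5 with:

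> Patients whose only events in a row are ungraded are counted in a 'grade missing' category, so that row totals match the any-grade tables. Patients with graded and ungraded events in a row are counted at the maximum recorded grade, and their number is given in a footnote. A sensitivity count of patients with Grade 3 or higher treats ungraded events as Grade 3 or higher, as a stated exception to Section 3.3.3.

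Apply the same rule to the by-severity rows of Section 6.3.1, so that the overall summary and the detailed tables are programmed alike.

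The category and the footnote are the essential part. They impute nothing and fit 3.3.3 as it stands. The category makes the totals reconcile; the footnote shows how many patients may be under-graded. The sensitivity count bounds the effect on severe events. Its Grade 3 cut-off is a convention, because nothing in the SAP fixes one, and it should be labelled as a worst case.

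The cost is one extra column, one footnote and a sensitivity figure that may be slightly less favourable than the main table. If every event is graded, the column is empty and no reported rate changes.

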### **6.3.6 Other Important Adverse Events**

AEs leading to death and study drug discontinuation will be presented in separate listings and the incidence will be summarized in the overall summary of TEAE table.

### **6.3.7 Adverse Events of Special Interest**

Summary of TEAEs, treatment-related AEs, and SAEs for diarrhea, rash, and stomatitis by MedDRA SOC and PT will be provided in separate tables with any grade and with Grade 3 or 4. Study day of first incidence for diarrhea, rash, and stomatitis will be summarized using median and range.

## **6.4 Laboratory Parameters**

The laboratory abnormalities will be classified for severity grade according to the NCI CTCAE version 4.03. Key laboratory parameters in hematology and blood chemistry will be summarized using shift tables, which display a cross-tabulation of the baseline grade versus the highest on-study grade for each laboratory parameter. Investigator evaluated clinical significance will be summarized for each parameter at each evaluation time point.

## **6.5 Vital Sign Data**

A summary of raw values and changes from baseline values will be provided at each scheduled time point for the following measurements: body temperature, systolic and diastolic blood pressure, and heart rate. A listing of all values will also be included.

## **6.6 ECOG Performance Status**

Descriptive statistics will be presented for ECOG scores baseline. The number and percentage of patients with shifts from baseline ECOG score (0, 1, or 2) to the worst post-baseline ECOG score (0, 1, 2, 3, or 4) will be summarized.

## **6.7 Other Safety Data**

Other safety data, including physical examination and cardiac assessment, will be provided in the data listings.

